2.3 Project Partners

A multidisciplinary team of six partners are committed to EDUCAT.

- ISEN-Lille – Technical University and lead partner¹²
- School of Engineering and Digital Arts, University of Kent¹³.
- East Kent Hospitals University NHS Foundation Trust¹⁴
- Sussex Community NHS Foundation Trust
- Catholic University Leuven - KU Leuven¹⁶
- VOKA – Chamber of Commerce of East Flanders¹⁷

2.4 Stakeholders

One of the key factors underpinning EDUCAT is the involvement of all stakeholders. These stakeholders will be involved in the development and evaluation of the system from project start to conclusion.

The stakeholders include wheelchair users, carers, service providers, clinicians, observer groups and industry.

The stakeholders committed to EDUCAT team are:

France:

CRN-T APF Association des Paralysés de France¹⁸

The Eurosanté Development Agency¹⁹

ESIGELEG University Rouen²⁰

United Kingdom:

Dynamic Controls²¹

Penny & Giles²²

Kent Brain Injury Forum (KBIF)²³

Sir William Beveridge Foundation (SWBF)²⁴

Belgium:

DSP Valley (a SME cluster)²⁵

3 Objectives

3.1 Stage 2 Main Objectives

The main objective is to obtain feedback from the participants on the value and efficacy of the obstacle alerting system. This feedback will be used to inform the ongoing development and specifications for the OAS.

This feedback will be obtained as follows.

Demographic Information: A brief questionnaire will be used to collect demographic information about the participants volunteering to take part in this stage.

Design and Development: Interviews using questionnaires will be conducted before and after the trial to obtain participant input to the specifications for the design and development of an assistive powered wheelchair, with special focus on the obstacle alerting system.

Evaluate Participant Driving Patterns with and without Obstacle Alerting: The impact of the presence of an obstacle alerting system will be investigated. Building on the initial experience from the Stage 1 trial the recorded data will be correlated with the participant's Daily Diary and their feedback on the value of the alerting system.

Typical parameters will be the frequency of use of the chair, the number of collisions, the participant's selection of feedback options and their satisfaction with those options.

For example the measurement of frequency of use of powered chairs and the speeds at which chairs are driven has been investigated by Cooper et al³⁴. This research focused on usage patterns rather than on how the user was driving the PWC. However, even knowledge of the environment in which the chair is driven, the way in which a chair is driven and the frequency with which it is driven can inform the clinician whether the user is confident in driving the chair. Lack of confidence and/or increased number of collisions can arise because the chair has not been set up to match the user's driving ability and/or that the user requires some driving assistance to mitigate these difficulties.

Monitoring driving patterns with and without the obstacle alerting system could provide evidence of the efficacy of that system. In turn this will help to develop a system that will help to improve user confidence and their level of independent mobility and quality of life.

Therefore the goal of Stage 2 is to use participant feedback to help develop a configurable obstacle alerting system which will help improve user independent mobility by enhancing their confidence and safety in driving a powered wheelchair.

Once the risks presented by COVID-19 are managed then the system can be evaluated by wheelchair users and their carers.

3.2 Secondary Objectives

Stage 1 and Stage 2 will also provide the foundation for:

- Stage 3 of the project. To assess:
 - the impact of driving assistance [Obstacle Avoidance] on the user's ability to drive more safely and with greater confidence.
 - whether the level of driving assistance provided by the PWC should be modified as the user's condition changes.

4 Study Design and Evaluation

4.1 Participants/Sample Size

10 adult non wheelchair users from staff of East Kent Hospitals NHS Foundation Trust [EKHUFT], Sussex Community Foundation Trust [SCFT] and the University of Kent

4.2 Location

The primary location for the trial will be the participant's place of work.

4.3 User Inclusion and Exclusion Criteria

Inclusion Criteria:

1. Adults who are not wheelchair users.
2. Willing and able to provide a valid consent
3. Able to participate in interviews aided or unaided using preferred method of communication.
4. Willing to drive a powered chair.
- 5.

Exclusion Criteria:

1. Lacks capacity to consent.

4.4 Length of User Involvement

Participants will drive one of the project teams PWC which have been fitted with the OAS.

Participants will have two options.

1. Drive the chair several time over a prescribed course with and without the Obstacle Alerting System active.

The whole process from familiarisation to the end of trial could take up to one day. The participant will have the option of spreading the trial over shorter periods of testing. This will depend on their work environment and work commitments.

2. Drive the chair over a period of up to 5 days.

Half the time with the system off and half with it on.

In practice this period may be a day or two shorter or longer dependent on the occurrence of weekends, the availability of participants and on their working patterns..

4.5 Recruitment:

Participants will primarily be recruited from within EKHUFT, SCFT and the University of Kent. All potential participants will be given the study Participant Information Sheet. They will then be contacted by the local research team to ask if they are interested. If they are interested a meeting will be arranged at a time and place suitable for the potential participant where consent will be received to participate. Optional consent to have photographs and video taken will also be received.

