Stage 2 Develop the Stage 1 system to include obstacle alerting. This system includes obstacle detection sensors e.g. infra-red, ultrasound and cameras, and a feedback system. The feedback system will have the options of auditory, haptic and visual information. This feedback will provide the user with information about the location and proximity of nearby objects. The hypothesis is that this information could help the user to drive more safely and confidently by being made aware of these objects.

The user is to evaluate this system.

Questionnaires will be used to collect user feedback before, during and after the each trial.

The anonymised data collected throughout the trial will be stored in local memory and also securely transmitted via the internet to the cloud.

The analysis of this data will be used to inform the on-going development of an obstacle alerting system which will help the user to drive more safely and confidently; thus enhancing the user's independent mobility and quality of life.

Stage 3: The Stage 2 system will be developed to use the information from the sensors to provide driving assistance by modifying the PWC trajectory to avoid collisions.

The efficacy of the system will be measured through analysis of the user's driving patterns, coupled with user interviews. This analysis will help to assess the effectiveness of this driving assistance system and provide feedback for the development of a user acceptable driving assistance system.

It is anticipated that the system developed by the end of Stage 3 will provide a basis for an assistive PWC that can be used for a range of tasks for PWC users including; improving user's access to independent powered mobility, monitoring changes in wellbeing and the effect of medication, monitoring progress during rehabilitation, training prospective users who may, with a driving assistance system, now be able to drive a PWC more safely and confidently.

The goal is to enhance the user's independent mobility and quality of life.

Because of the challenging nature of this project Ethics and HRA approval are being applied for stage by Stage.

Stage 1 is now underway [IRAS ID 235049].

This study protocol relates to **Stage 2** where, because of the impact of COVID-19, the participants will no longer be powered chair users but adults who are not wheelchair users.

As the project technology is developed it is planned to submit an application for Stage 3.

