4.8.5.2 Driving Training

The participant will take part in a familiarisation session so that they can learn to drive the PWC.

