4.8.5.3 Familiarisation with the Obstacle Alerting System

The participant will be familiarised with the OAS. This will include:

- Overview of the system
- Training on how to enable and disable audio, visual and haptic feedback options
- Driving the chair with feedback provided around a prescribed course
- Configuration of the feedback options to suit the wheelchair user
- Reminder of how to adjust this configuration during the trial to suit their environment and preferences
- Operation of the data input device to access the Daily Diary.

The participant will use this familiarisation to inform the team of their preferences for setting up the OAS in terms of sensitivity to objects and the preferred feedback mode.

The participant will be provided with a user manual and an information sheet telling them what to do and who to contact in case of faults with the system or any other questions.

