4.7.6.3 Data Recording

The participant will have the choice of which study protocol they wish to follow. Data will be recorded with the OAS feedback turned off and turned on.

This allows the collection of comparative data on how the obstacle alerting system may influence and affect aspects of driving, including confidence in different environments.

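### Option 1 repeats a prescribed course with the OAS off and on and states no alternate layout or run order, so course knowledge is confounded with the OAS effect on driving

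*Protocol*

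**What the plan says.** Protocol 4.4 offers two ways of taking part. In Option 1 participants "Drive the chair several time over a prescribed course with and without the Obstacle Alerting System active", and "The whole process from familiarisation to the end of trial could take up to one day", although the participant may spread it over shorter sessions. Option 2 is driving over up to 5 days, "Half the time with the system off and half with it on", and mentions no prescribed course. On who does which, 4.7.6.3 says "The participant will have the choice of which study protocol they wish to follow".

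Before recording starts there are two preparatory steps. In 4.8.5.2, "The participant will take part in a familiarisation session so that they can learn to drive the PWC". In 4.8.5.3, familiarisation with the OAS includes "Driving the chair with feedback provided around a prescribed course".

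On the comparison itself, 4.7.6.3 says "Data will be recorded with the OAS feedback turned off and turned on" and gives no sequence. Section 3.1 expects the off/on comparison of driving patterns to be possible evidence of efficacy and names the number of collisions among the parameters. Section 2.1 states how the OAS should work: "The hypothesis is that this information could help the user to drive more safely and confidently by being made aware of these objects".

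**The concern.** The OAS is meant to help by making the driver aware of objects. A driver who has been round the same course several times has gained part of that awareness from memory, with the system on or off. Participants are also novices, so their driving skill is likely to improve over the same runs. With one course and no stated order, three things move together: condition, knowledge of the course, and practice.

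At stake is what the Option 1 driving data can show. An off/on difference in collisions, smoothness or joystick displacement could be smaller or larger than the OAS effect, or of opposite sign, and the data would not reveal which. This is settled when the runs are driven. If every recorded run uses one layout, no later analysis can produce off-runs by drivers who do not know it.

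**Working it through.** **What the protocol fixes.** It gives 10 participants (4.1), no split between the options, no number of runs beyond several, and no effect size or variability. There is no planned figure to reproduce, so the check concerns the direction of bias. All inputs below are assumptions.

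**Model.** Expected errors in run k (k = 0 to 5) with the OAS off are b(1 - f)q^k. With the OAS on they are multiplied by (1 - e).

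- b = 1: errors per run for a driver new to the course.
- f: share of errors already removed by course knowledge before the first recorded run. f = 0 fits a familiarisation course different from the test course.
- q: share of errors remaining from one run to the next, through course learning and practice together.
- e: true relative reduction from the OAS.
- Three off-runs and three on-runs.

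**Step 1: prior knowledge only (q = 1).** The absolute difference is b × e × (1 - f). With e = 0.30:

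- f = 0: 0.30
- f = 0.3: 0.30 × 0.7 = 0.21
- f = 0.6: 0.30 × 0.4 = 0.12

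This holds in either order. The relative reduction stays at 30%, because on-runs gain from the knowledge as much as off-runs do.

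**Step 2: learning across runs (e = 0.3, f = 0.3, q = 0.8).** The mean of (1 - f)q^k is 0.7 × (1 + 0.8 + 0.64)/3 = 0.569 over the first three runs and 0.7 × (0.512 + 0.4096 + 0.3277)/3 = 0.292 over the last three.

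| Order | Mean off | Mean on | Off minus on | Relative reduction |
|---|---|---|---|---|
| Off first | 0.569 | 0.7 × 0.292 = 0.204 | 0.37 | 64% |
| On first | 0.292 | 0.7 × 0.569 = 0.399 | -0.11 | -37% |
| Counterbalanced | 0.430 | 0.301 | 0.13 | 30% |

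The true values are 0.30 and 30%.

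**Step 3: other assumed values.**

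- f = 0, q = 0.8: the absolute differences are 0.52, -0.15 and 0.18 in the same three rows, with the relative figures unchanged. The dependence on order therefore does not need the two courses to be the same.
- f = 0.6, q = 0.8: off first gives 0.21, below the true 0.30, while the relative reduction is still 64%. The two scales can point in opposite directions.
- q = 0.9: 49% off first, 4% on first.
- q = 0.7: 76% off first, -104% on first.
- e = 0.5, q = 0.8: 74% off first, 2% on first.

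**Step 4: is counterbalancing enough?** Step 2 assumes that on-runs and off-runs teach the course equally fast. Suppose instead that 0.7 of errors remain after an on-run and 0.85 after an off-run (e = 0.3, f = 0), with one run per condition.

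- Off first: off = 1, on = 0.85 × 0.7 = 0.595.
- On first: on = 0.7, off = 0.7.
- Averages: off 0.85, on 0.6475. The difference is 0.20 and the relative reduction 24%.

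With three runs per condition the figures are 0.16 and 28%. The relative loss is modest, but counterbalancing alone need not remove it.

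**The case against.** The strongest reply is that memory of a course does not replace the OAS. Section 2.2.3 describes information on objects within 2 metres and gives a door frame or a wall as an example of something struck. Section 2.2.5 describes vibration graded by proximity and a reversing camera. Such collisions can be misjudged clearances by a driver who knows perfectly well that the object is there. This stands: course knowledge overlaps with what the OAS supplies, only in part, and the protocol gives no figure for the overlap.

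Second, this is a preliminary evaluation whose main objective is participant feedback (3.1, 4.9.1). No test or decision rule is attached to the driving comparison. This also stands and limits the weight of the point. It does not remove it, because 3.1 still looks to that comparison for evidence of efficacy.

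Three stronger readings are tempting, and the documents do not support them.

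- A reader might infer that carry-over hides the benefit whatever the order. Course knowledge also helps the on-runs, and if these come second it can exaggerate the benefit.
- A reader might infer that the familiarisation course is the Option 1 course. Both sections speak only of a prescribed course and neither refers to the other. If they differ, the first recorded run is new to the driver and learning begins from there.
- A reader might take the shrinkage in Step 1 as a loss of relative effect. It is an absolute difference against a driver new to the course; if knowledge helps equally off and on, the relative reduction is unchanged.

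**Conclusion.** The point holds for the driving comparison in Option 1 only. A prescribed course is repeated off and on, possibly within a day of an OAS-on familiarisation drive, and neither a change of layout nor an order of conditions is stated. Course learning is therefore confounded with the OAS effect. Knowledge of the layout shrinks the absolute off/on difference. The net bias depends on order: exaggeration (at least on the relative scale) if off-runs come first, masking or reversal if on-runs come first.

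The sizes (64%, -37%, and 0.13 in place of 0.30) rest wholly on assumed learning rates and an assumed OAS effect, and show only that the bias could be as large as the effect sought. Option 2 has no prescribed course, and the questionnaire feedback is not an off/on comparison of this kind, so neither is affected. Nor do the documents support predicting that the trial would conclude the OAS makes no difference, since no such conclusion is planned. This is an inexpensive improvement to a supporting comparison, worth making before data are collected.

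**What to change.** Amend 4.4 and 4.8.5.3 as follows.

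1. Carry out the OAS familiarisation drive on a course or layout that is not used for recorded runs.
2. Use at least two matched layouts for recorded Option 1 runs, of similar length and number of obstacles, each used equally often with the OAS off and on across participants.
3. Counterbalance the order of off and on across participants. New layouts alone would leave driving practice confounded with condition.
4. Record the layout and the run number with each run.

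With two layouts A and B and two conditions, the basic scheme has 2 × 2 = 4 sequences: off-A then on-B, off-B then on-A, on-A then off-B, on-B then off-A.

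The cost is some set-up time at each site, two extra data fields, and some added variation because layouts will not be equally difficult. Participants choose their option and there are 10 in all, so the number in Option 1 is unknown. With few of them, layout difficulty and order may not balance fully, which is a further reason to record both. No additional participants are needed.

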4.6 Participant Anonymity

Participant identification will be pseudonymised.

Personal information will be kept on secure servers within the relevant NHS organisation.

Pseudonymised information will be kept on the secure servers of EKHUFT, the University of Kent, SCFT and of the French and Belgian partners.

4.7 Information and consent sheets

Participants will be issued with information and consent sheets.

- Participant Information Sheet
- Participant Consent Form
- Participant Image Consent Form

4.8 Questionnaires:

4.8.1 Enrolment Forms

The purpose of this form is to obtain or check demographic information. The participants will be issued unique ID code for use in the pseudonymised questionnaires.

These forms will be paper based and stored in a secure location at the relevant NHS partner organisation.

4.8.2 Pre-trial Questionnaires

The purpose is to obtain or verify the wheelchair user's medical information and to obtain their views on the possible configuration and value of an OAS. The questionnaire includes open ended questions to elicit preferences for the configuration of the system for their use during the trial.

Experience from Stage 1 shows that wheelchair users who are engaged in the project want to discuss in detail their experiences and ideas. Therefore the time to complete the interview can be approximately 1 hour.

4.8.3 Daily Diary

The participant will be asked to fill out the Daily Diary for the time periods that they are using the powered chair. The information from this diary will be used to correlate participant opinion of the OAS, their driving patterns and any changes due to those patterns with their:

- Feeling of wellbeing
- Level of Pain
- Taking of medication
- Environment in which they are using the PWC
- Opinion of the powered wheelchair
- Evaluation of the OAS – deficits and areas for improvement.

The diary will be completed using the CCU tablet. A paper version will be available as a backup. It is hoped that the use of an electronic diary will facilitate/encourage the entry of data by the participant and aid the analysis of the data from the OAS.

4.8.4 Post-Trial Questionnaire

At the end of the stage 2 trial the participant will be asked to provide their feedback on the obstacle alerting system and on the trial design.

This questionnaire will be face to face and conducted by the project team staff.. This should take less than 60 minutes.

4.8.5 Study Design

The trial will take place at the partner sites [EKHUFT, SCFT and the University of Kent]. The PWC will be provided by the study team and configured to suit the participant.

4.8.5.1 Pre-trial Enrolment Form

The enrolment form (4.7.1 & 2) will be completed.

4.8.5.2 Driving Training

The participant will take part in a familiarisation session so that they can learn to drive the PWC.

4.8.5.3 Familiarisation with the Obstacle Alerting System

The participant will be familiarised with the OAS. This will include:

- Overview of the system
- Training on how to enable and disable audio, visual and haptic feedback options
- Driving the chair with feedback provided around a prescribed course
- Configuration of the feedback options to suit the wheelchair user
- Reminder of how to adjust this configuration during the trial to suit their environment and preferences
- Operation of the data input device to access the Daily Diary.

The participant will use this familiarisation to inform the team of their preferences for setting up the OAS in terms of sensitivity to objects and the preferred feedback mode.

The participant will be provided with a user manual and an information sheet telling them what to do and who to contact in case of faults with the system or any other questions.

4.7.6.3 Data Recording

The participant will have the choice of which study protocol they wish to follow. Data will be recorded with the OAS feedback turned off and turned on.

This allows the collection of comparative data on how the obstacle alerting system may influence and affect aspects of driving, including confidence in different environments.

4.9 Outcome Measures

4.9.1 Analysis of Questionnaires

The main goal of this stage is to obtain participant feedback on the design and value of the OAS.

This information will be fed into the ongoing refinement of Stage 2 and the development of Stage 3 of the project.

Participant feedback will also be used to refine the information sheets, questionnaires and Daily Diary.

4.9.2 Driving Data Analysis

The recorded data will be analysed to examine the correlations between:

- Time and Date
- Joystick Movement Smoothness²⁶⁻²⁸
- Joystick Displacement patterns
- PWC collisions
- Time spent driving the chair
- Use of Actuators
- Location of the chair

- Daily Diary information [4.8.3]

4.9.3 Driving data Analysis Correlation with Daily Diary Information

This driving analysis data will be correlated with the information recorded in the Daily Diary - reported wheelchair participant wellbeing, medication, location in which the PWC is being driven and impact/usefulness of the OAS - over the intervals of morning, afternoon, evening and night. This information will be used for future trials with wheelchair users. The data analysis software developed with normal participants will be used in the on-going evaluation of the hypothesis that:

- each wheelchair user has their own driving characteristics which also depend on wheelchair user
 - wellbeing
 - medication
 - environment/location

and that these characteristics and changes in these characteristics can

- identify the wheelchair user
- inform the wheelchair user and clinician about wheelchair user health and changes in health
- monitor the effect of medication – if any
- monitor the impact of the OAS

